7.2 General Methodology

All data analyses will be performed by Medtronic or its designee. All statistical analyses will be performed using the Statistical Analysis System (SAS) for Windows (version 9.4 or higher, SAS Institute Inc. Cary, NC), R (version 4.0.0 or higher), or other widely accepted statistical or graphical software.

Descriptive statistics will be used to summarize study outcomes. Continuous variables will be summarized using number of subjects (n), mean, standard deviation, median, interquartile range (IQR), and ranges. Categorical variables will be summarized using frequencies and percentages. Confidence intervals may be produced for either continuous or categorical variables as warranted.

All tests of treatment effects will be conducted at a two-sided alpha level of 0.05 unless otherwise stated. A p-value less than 0.05 is considered statistically significant. Confidence intervals will be presented at the 95% level unless otherwise stated.

The study safety and performance analyses will occur after all subjects complete the 30-day follow-up. The analyses will include both primary and secondary objectives which are related to 30-day follow-up. A CSR will be prepared once all data collection has ended and all subjects have completed the 30-day follow-up or have exited. Annual progress reports will be prepared for oncologic subjects through 5 years. A final report will be completed at the end of the 5-year follow-up.

7.3 Center Pooling

Study centers will be pooled together for all planned analyses as they are assumed to be homogeneous in terms of clinical practice, efficacy and safety. This assumption will be tested for the primary efficacy endpoint as later described in **Section 7.9.1.7.1**.

7.4 Handling of Missing, Unused, and Spurious Data and Dropouts

The primary analysis will be based on the full analysis set with no imputation of missing data. For secondary objectives, analyses will be conducted using subjects with available data from the FAS. Sensitivity analyses will be performed for the primary endpoints using multiple imputation for missing data when the missing percentage is greater than 5% as well as tipping-point analysis on the primary effectiveness endpoint to fully understand the missing data impact on the study results.

7.5 Adjustments for Multiple Comparisons

For the primary effectiveness endpoint only one hypothesis will be tested at an alpha of 0.025 one-sided. If the one-sided primary objective p-value is <0.025, then the null hypothesis will be rejected, and the test will be declared statistically significant.

After the primary effectiveness objective is met, the primary safety objective for each surgery type will be tested as described in **Section 7.9.2.1**. For the primary safety endpoint (major complication rate), the closed test procedure (Holm's method, i.e. Holm-Bonferroni method) will be used to protect the overall study-wise error rate for surgery types (nephrectomy, prostatectomy and cystectomy).¹

The Holm-Bonferroni method is applied in context of this study as follows: start by listing all the p-values obtained from the multiple statistical tests and arranging them in ascending order, from the smallest to the largest. For each ordered p-value, calculate a sequentially adjusted significance level using the formula ($\text{alpha}(i) = 0.025 / (3+1-i)$), where '0.025' is the desired overall significance level, '3' is the total number of tests, 'i' is the rank of the p-value in the ordered list, and 'alpha(i)' is the adjusted significance level for test 'i'. Next, compare each p-value with its adjusted significance level, starting with the smallest p-value. If the smallest p-value is less than or equal to alpha(1), reject the null hypothesis for the first test and move to the next smallest p-value, comparing it to alpha(2). Continue this process sequentially for each p-value. As soon as a p-value is greater than its corresponding adjusted significance level alpha(k), the procedure is stopped and the remaining p-values for the null hypotheses are not rejected. The null hypotheses corresponding to the p-values that were rejected are considered statistically significant, while those corresponding to the p-values that were not rejected are not considered statistically significant. The Holm-Bonferroni method is more powerful than the simple Bonferroni correction because it adjusts the significance levels in a stepwise manner, making it less conservative.

There will be no multiplicity controls applied to the secondary endpoints as strict hypothesis testing is not being utilized.

7.6 Demographic and Other Baseline Characteristics

Subject demographics, medical, and surgical history will be summarized using descriptive statistics for continuous variables (number of observations, mean, standard deviation, median, IQR, and ranges) and frequency tables for discrete variables.

Age will be reported in years. Subjects with available data will be summarized; gender will be summarized using counts and percentages. In addition to the reported values, unknown or unreported values will also be in the summaries as a count of subjects (if any). The supportive data for the demographics table will be presented in a listing entitled "Subject Demographics".

Summary of procedural characteristics including procedure time, primary diagnosis, and robotic performance will be presented.

7.7 Treatment Characteristics

A descriptive data summary for surgical procedure characteristics and exposure to the study device will be provided. Summaries will be discussed in the study report.

7.8 Interim Analyses

No interim analysis is planned for this study. Outcomes through 30 days for the first 15 roll-in cases will be summarized descriptively and provided to the FDA for initial review without statistical inferences. The roll-in subjects will be included in the final data analysis for the study.

7.9 Evaluation of Objectives

7.9.1 Primary Effectiveness Objective

The primary effectiveness endpoint is the surgical success rate, defined as the procedure not going into conversion. Conversion is defined as the switch from a robotic-assisted approach using the Hugo™ system to a robotic-assisted approach utilizing an FDA cleared robotic-assisted device, laparoscopic or open surgery.

7.9.1.1 Hypothesis

The primary effectiveness hypothesis is to test if the surgical success rate is above the performance goal. Based on the Clinical Data Analysis of Robotic-Assisted Surgical Procedures in Urology Rev B (Medtronic on file), henceforth referred to as the Urology Clinical Data Analysis and clinical practice, a surgical success rate of 90% or higher is expected. To account for natural variability between sites, surgeons, and surgery types an overall performance goal of 85% (based on the literature) is pre-defined to evaluate the surgical success rate. Let P be the surgical success rate in this study. The statistical hypothesis is as follows:

$$H_0: P \leq 85\% \quad \text{vs.} \quad H_a: P > 85\%$$

7.9.1.2 Endpoint Definition and Derivation

Sites are asked if the procedure was completed according to the surgical plan (Yes/No). If the answer was "No", they had to specify what was not done per the surgical plan. If the site specifies "Converted" as what was not done per the surgical plan, then the surgery is identified as a conversion. Surgical success is defined as a surgery that has not been specified as a conversion. The proportion of subjects with a successful surgery needs to meet a performance goal of 85%.

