10.1.5 Post-Operative Follow-Up Visits (Visit 4-8)

Post-operative visits 4-8 for oncologic subjects will be made via a phone call to assess overall survival, progression-free survival, and disease-free survival.

Medtronic Expand URO Clinical Investigation Plan

MDT19051EINURO

Version 9.0

Page 40 of 111

Medtronic

Table 6. Data Collection and Study Procedure Requirements at Subject Visits

Procedure/Assessment	Screening (Day -30 to 0) Visit 1	Surgical Procedure (Day 0) Visit 2	Hospital Discharge Visit 2.1	Follow-Up (30+7 Days) Visit 3	Follow-up (Years 1 - 5) (+/- 3 mo. window) Visits 4-8
	May be Combined				
Informed Consent Form ¹	X	X			
Eligibility Criteria	X	X			
Demographic Data	X				
Medical/Surgical History	X				
Concomitant Medication(s)	X	X	X	X	
Lab Values (if applicable)	X	X	X	X	
Robot Setup Time		X			
Total Operative Time (skin to skin)		X			
Surgeon Console Time		X			
Instruments Used		X			
Estimated Blood Loss		X			
Transfusion ³		X	X	X	
Conversion to a robotic-assisted approach utilizing an FDA cleared robotic-assisted device, open or manual laparoscopy		X			
Robot Take Down Time		X			
Warm Ischemia Time (if applicable)		X			
Anastomotic Leak Test performed (if applicable)		X			
Anastomotic Stricture (if applicable)		X			
Rate of Positive Circumferential Margins on Final Pathology (if applicable)		X			
Margin (mm) (if applicable)			X		

Medtronic Business Restricted

This document is electronically controlled

CONFIDENTIAL 056-F275 Rev E Clinical Investigation Plan Template

Medtronic Expand URO Clinical Investigation Plan

MDT19051EINURO

Version 9.0

Page 41 of 111

Medtronic

Procedure/Assessment	Screening (Day -30 to 0) Visit 1	Surgical Procedure (Day 0) Visit 2	Hospital Discharge Visit 2.1	Follow-Up (30+7 Days) Visit 3	Follow-up (Years 1 - 5) (+/- 3 mo. window) Visits 4-8
Tumor Size (if applicable)			X		
Tumor Stage (if applicable)			X		
Total number of lymph nodes retrieved			X		
Catheterization Time			X	X	
Mortality			X	X	X
Length of Hospital Stay			X		
Reoperation			X	X	X
Pain Medication			X	X	
Medications if associated with an AE	X	X	X	X	X
Adverse Events ²	X	X	X	X	X
Readmission				X	X
Device Accountability		X			
Device Deficiency		X			
Protocol Deviation Collection (if applicable)	X	X	X	X	X
Study Exit				X	X

¹Study specific procedures may only be performed after subject has agreed to participate and signed the informed consent form.

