Medtronic is responsible for analyzing deviations, assessing their significance, and identifying any additional corrective and/or preventive actions (e.g., amend the CIP, conduct additional training, terminate the investigation). Repetitive or serious Investigator compliance issues may result in initiation of a corrective action plan with the Investigator and study site, and in some cases, may necessitate suspending enrollment until the problem is resolved or ultimately terminating the Investigator's participation in the study. Medtronic will provide study site-specific reports to Investigators summarizing information on deviations that occurred at the investigational study site on a periodic basis.

If during the procedure, the Investigator changes from HUGO™ to another RAS system (even if it is in conjunction with HUGO™), it will no longer be a protocol deviation, but it will be captured as a device deficiency as needed/applicable. If the Investigator converts to laparoscopic or open surgery, it will not be considered a protocol deviation.

Examples of study deviations include but are not limited to:

- Failure to obtain proper IC
- Failure to collect required study data
- Inclusion/exclusion criteria not met

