7.9.1.6 Determination of Subjects/Data for Analysis

The analysis of the primary effectiveness will be based on the FAS but following the mITT principle for the conversion endpoint by excluding any subject with that endpoint missing.

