7.9.1.7.3 Sub-group Analysis by Surgery Type

The surgical success rate for each surgery type will be calculated as the proportion of subjects with a successful surgery, with a one-sided 97.5% confidence lower bound. Additionally, a summary of type of conversion (open, laparoscopic, or other RAS) will be provided.

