7.9.3.1 Objectives, Endpoint Definitions and Derivations

Endpoint #	Objective	Endpoint Definition and Derivation
1	Overall Complication Rate	Rate of overall complications within 30 days is calculated as the proportion of subjects who experience any related (device, procedure, or underlying condition/disease) adverse event prior to or during the 30 calendar-days post-procedure. The AE start date collected with the adverse event will be used to determine whether a complication was experienced.
2	Operative Time	Operative time is defined as the difference in time in minutes between the procedure end time and the procedure start time. The procedure start time is the time of first incision and the end time is the time of skin closure.
3	Intraoperative Estimated Blood Loss	The estimated amount of blood loss is reported during the procedure in mL.
4	Transfusion Rate	Occurrence of a blood transfusion is captured as an adverse event. A blood transfusion is defined as an AE that resulted in any treatment and then a bleeding complication led to a blood transfusion and started prior to or during the 30 calendar-days post-procedure.
5	Device-related Conversion	A conversion is defined the same way as in Section 7.9.1.2 . A device related conversion is defined as a conversion where either the primary or any other reason for conversion is denoted as Adverse Event that is related to the device or procedure, Device Deficiency, Non-Subject Adverse Event, or Poor Visualization.

6	Hospital Length of Stay	
The length of hospital stay is the number of days that the subject was in the hospital from the start of the surgical procedure to hospital discharge. The number of days in the hospital can be found as the difference in minutes between the discharge date and time and the procedure date and time divided by 1440 min/hour, i.e.,
 $(Discharge Date and time - procedure date and time)/1440.$
7	Readmission Rate	A readmission in a subject is identified if a related (device, procedure, or underlying condition/disease) adverse event with a start date of or after the index procedure date and prior to or during the 30-calendar days post-procedure that resulted in the subject being hospitalized. Additionally, the hospital start date reported within the AE must be prior to or during the 30 calendar-days post-procedure and on or after the reported index procedure discharge date.

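### A Hugo procedure abandoned after first incision, without a switch to another approach, is scored as a surgical success in the primary effectiveness test

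*SAP*

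**What the plan says.** **The endpoint.** Protocol 5.1.3 and SAP 7.9.1 agree. The endpoint is "the surgical success rate, defined as the procedure not going into conversion", and conversion is a switch from Hugo to another FDA-cleared robot, laparoscopy or open surgery.

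**The derivation.** SAP 7.9.1.2 describes a two-step site response. The site states whether the procedure was completed according to the surgical plan. If not, it specifies what was not done. If it gives Converted "as what was not done per the surgical plan, then the surgery is identified as a conversion". Everything else falls under "Surgical success is defined as a surgery that has not been specified as a conversion".

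**The population.** SAP 7.1.3 puts every enrolled subject into the FAS once the first skin incision for a Hugo procedure is made. SAP 7.9.1.6 then removes subjects whose conversion endpoint is absent, by "excluding any subject with that endpoint missing".

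**Switch to another robot.** Protocol 10.8 says of a change to another RAS system, even one used together with Hugo, that "it will no longer be a protocol deviation, but it will be captured as a device deficiency as needed/applicable". Elsewhere the same event is a conversion:
- Table 6 (Protocol 10.1.5) lists at Visit 2 "Conversion to a robotic-assisted approach utilizing an FDA cleared robotic-assisted device, open or manual laparoscopy".
- SAP 7.9.1.7.3 says "a summary of type of conversion (open, laparoscopic, or other RAS) will be provided".
- For device-related conversion, SAP 7.9.3.1 accepts cases where the "reason for conversion is denoted as Adverse Event that is related to the device or procedure, Device Deficiency" or certain other causes.

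**The concern.** A rule that defines failure by one specific response, and success as all the rest, is safe only if that response covers every way the procedure can fail. Here it does not. A Hugo case stopped after incision and not continued by any other approach involves no switch, so a site that follows the definition would not choose Converted. The derivation then scores it as a success, although the procedure was never completed with the device.

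The error can run in only one direction, towards the device, in a single-arm trial where the site's own response decides the endpoint. The Clinical Events Committee adjudicates deaths, related serious events and Grade III and IV complications (Protocol 12.1); conversion is not on that list. The sensitivity analyses in SAP 7.9.1.7.2 deal with missing outcomes, and an abandoned case with a completed form is not missing.

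The wording of Protocol 10.8 adds a smaller risk: a site that reads that clause alone could complete the device-deficiency form and not record the conversion.

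**Working it through.** **1. How each type of case is scored under the text as written**

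| Case in the FAS | Score | Basis |
|---|---|---|
| Completed on Hugo, plan followed | Success | SAP 7.9.1.2 |
| Completed on Hugo, plan changed in some other respect | Success, as intended | SAP 7.9.1, 7.9.1.2 |
| Switched, logged as Converted | Failure | SAP 7.9.1.2 |
| Switched to another robot, recorded only as a device deficiency | Success, contrary to intent | Protocol 10.8 read alone |
| Abandoned after incision, no switch | Success | SAP 7.9.1.2 with 7.1.3 |
| Endpoint missing | Excluded | SAP 7.9.1.6 |

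**2. Reproducing the plan's power figure**

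Inputs: goal 85%, one-sided alpha 0.025, exact test, n=126 after 10% attrition from 141 (Protocol 14.4.1); expected success rate 95.2% (Protocol 14.7, SAP 6).

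The pass mark is the smallest r with P(X ≥ r | n, 0.85) ≤ 0.025.
- n=126: r=116, so at most 10 failures. Exact size is 0.0131. Power at 95.2% is P(X ≥ 116 | 126, 0.952) = 0.9595, which matches the stated 0.96.
- n=141: r=129, so at most 12 failures. Exact size is 0.0157 and power 0.981.

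**3. What rescored cases do at the pass mark**

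The p-value is P(failures ≤ k | n, 0.15).

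| n | Failures k | Success rate | p | Result |
|---|---|---|---|---|
| 126 | 10 | 92.1% | 0.0131 | pass |
| 126 | 11 | 91.3% | 0.0265 | fail |
| 126 | 12 | 90.5% | 0.0492 | fail |
| 141 | 12 | 91.5% | 0.0157 | pass |
| 141 | 13 | 90.8% | 0.0300 | fail |
| 141 | 14 | 90.1% | 0.0529 | fail |

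One rescored case changes the conclusion if the logged count is exactly at the limit.

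**4. How likely the boundary is**

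At the expected 4.8% failure rate, 141 × 0.048 = 6.8 failures are expected. From 7 logged failures, six more are needed to reach 13. The chance that logged failures fall between 10 and 12 of 141, where one to three extra failures would overturn a pass, is 0.12 at a 4.8% failure rate. At the 2.2% mean conversion rate in Protocol 14.4.1 it is about 0.001.

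**5. Effect on the error rate, over an assumed range**

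The documents give no rate of abandoned or unlogged cases, so the shares below are assumptions. Suppose the true rate of completion on Hugo is exactly 85%, and a share u of all cases is not completed on Hugo but scored as success. The chance of passing is P(X ≥ r | n, 0.85 + u).

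| u | n=126 | n=141 |
|---|---|---|
| 0 | 0.013 | 0.016 |
| 1 point | 0.027 | 0.033 |
| 2 points | 0.053 | 0.066 |
| 3 points | 0.098 | 0.123 |
| 5 points | 0.275 | 0.338 |

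From 1 point upwards, the chance of passing exceeds the nominal 0.025.

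**The case against.** The strongest reply is that the derivation implements the endpoint as defined. Both documents define success as no conversion and conversion as a switch, and the 85% goal was built from published conversion rates (Protocol 14.4.1, SAP 7.9.1.4). Counting abandonment as failure widens the numerator without moving the benchmark. This is fair, and it means the abandonment gap is not a contradiction between SAP and protocol: neither document addresses the case. It does not settle how such a case should count in a test meant to confirm effectiveness.

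A reader might also infer four stronger points. The documents do not support them.
- **That blank answers count as successes.** SAP 7.9.1.6 excludes them, and SAP 7.9.1.7.2 adds a tipping-point analysis, multiple imputation above 5% missing and a listing.
- **That every departure from the surgical plan is a misrouted failure.** A plan can change while the case is finished on Hugo; that remains a success.
- **That a switch to another robot is meant to count as a success.** The endpoint definition, Table 6 and the conversion-type summary all make it a conversion, and device deficiency is an accepted reason for one. Protocol 10.8 concerns deviations and does not say the deficiency record replaces the conversion record. A case is lost only if a site follows that clause alone.
- **That the SAP ignores the Table 6 conversion item.** Table 6 lists assessments, not form fields. The Converted response may be how that item is captured.

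**Conclusion.** The point stands in a limited form. Followed exactly, SAP 7.9.1.2 scores a Hugo procedure abandoned after incision without a switch as a success, and no planned analysis shows what difference that makes. Protocol 10.8 needs to be tied to the conversion definition, but that is a reporting risk and not a rule that reclassifies switches.

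No stated figure is wrong; the power of 0.96 is reproduced. The practical effect depends on how close the result is to the limit of 12 failures in 141, or 10 in 126. If failures run near the expected 4.8%, a few abandoned cases would probably not change the conclusion. The error-rate figures rest on an assumed share of 1 to 5 points and a true completion rate of exactly 85%, and should be read as a range, not a forecast. The gap deserves correction because it concerns the primary endpoint, can only favour the device and is cheap to close.

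**What to change.** 1. In SAP 7.9.1.2, state that a FAS procedure begun but not completed with Hugo, whether abandoned or switched to another robot, laparoscopy or open surgery, is not a surgical success. Put the same rule in the protocol's endpoint definition. At minimum, keep the current derivation as primary and pre-specify a sensitivity analysis that scores such cases as failures.
2. Say explicitly that a procedure completed on Hugo with some other change to the surgical plan remains a success. Leave the exclusion of missing endpoints as it is.
3. Before analysis, check the Converted response against the Table 6 conversion item and the device-deficiency records, and resolve any mismatch.
4. In Protocol 10.8, cross-refer to the conversion definition, so that recording a device deficiency does not replace recording the conversion.

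The cost is wording in both documents and one reconciliation check, with no change in sample size. The success rate may come out slightly less favourable, and the failure definition becomes slightly broader than the conversion rates behind the 85% goal. The report should state that second point, or the sensitivity-analysis route can be used to keep the primary test aligned with its benchmark.

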7.9.1.3 Performance Requirements

The null hypothesis will be rejected if the p-value for the one-sided hypothesis test is less than 0.025 or, equivalently, the one-side 97.5% lower confidence bound is greater than 85%.

7.9.1.4 Rational for Performance Criteria

Analyses were performed based on available literature. Point estimates along with 95% and 99% predicted intervals were calculated to provide plausible ranges of potential effect sizes. Clinically meaningful margins and statistical precisions have been taken into account to determine the appropriate performance goals.

The mean effect size for conversions is 0.024 with a 95% confidence interval of 0.019 to 0.032. The 95% prediction interval is 0.004 to 0.125. The 99% prediction interval is 0.003 to 0.20. A performance goal of 85% for surgical success rate was set, which is equivalent to 0.15 as the conversion rate (1-success rate), aligned with the 95% to 99% of predictive intervals upper limit of 0.125 to 0.2. A single-group design will be used to test whether the proportion is greater than 0.85 ($H_0: P \leq 0.85$ vs. $H_1: P > 0.85$).

